6.2.3.2 Events of Clinical Interest

Selected non-serious and serious adverse events are also known as Events of Clinical Interest (ECI) and must be reported within 24 hours to the Sponsor and within 2 working days to Merck Global Safety. (Attn: Worldwide Product Safety; [contact]).

For the time period beginning when the consent form is signed until treatment allocation/randomization, any ECI, or follow up to an ECI, that occurs to any subject must be reported within 24 hours to the Sponsor and within 2 working days to Merck Global Safety if it causes the subject to be excluded from the trial, or is the result of a protocol-specified intervention, including but not limited to washout or discontinuation of usual therapy, diet, placebo treatment or a procedure.

For the time period beginning at treatment allocation/randomization through 90 days following cessation of treatment, or 30 days following cessation of treatment if the subject initiates new anticancer therapy, whichever is earlier, any ECI, or follow up to an ECI, whether or not related to Merck product, must be reported within 24 hours to the Sponsor and within 24 hours to Merck Global Safety.

Events of clinical interest for this trial include:

1. an overdose of Merck product, as defined in Section 7.2.1 - Definition of an Overdose for This Protocol and Reporting of Overdose to the Sponsor, that is not associated with clinical symptoms or abnormal laboratory results.
2. an elevated AST or ALT lab value that is greater than or equal to 3X the upper limit of normal and an elevated total bilirubin lab value that is greater than or equal to 2X the upper limit of normal and, at the same time, an alkaline phosphatase lab value that is less than 2X the upper limit of normal, as determined by way of protocol-specified laboratory testing or unscheduled laboratory testing.*

***Note:** These criteria are based upon available regulatory guidance documents. The purpose of the criteria is to specify a threshold of abnormal hepatic tests that may require an additional evaluation for an underlying etiology.

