3.2.3 Rationale for Endpoints

3.2.3.1 Efficacy Endpoints

Primary endpoint: percentage of patients that have not progressed at 1 year using immune related radiological criteria (see section 11.3). The 1 year timing relates to the time from trial enrolment and initiation of pembrolizumab as maintenance therapy. This is the most clinically relevant endpoint in a maintenance study. Prolongation of disease control is a very worthwhile endpoint, towards the realization of the goal to obtain long term disease control for patients with metastatic NSCLC, similar to the results seen with checkpoint inhibition for patients with melanoma. The timing of assessment at 1 year is based on the durable nature of responses seen with Pembrolizumab so far, suggesting that at 1 year there is going to be a large difference in disease progression between patients on Pembrolizumab compared to the historical data from the maintenance studies.

Secondary Endpoints: These would include

- Response rates (RECIST)
- Response Rates with immune related Response Criteria (irRC)
- Radiological Progression Free Survival (PFS) using RECIST criteria
- Immune-related PFS using irRC: irPFS is the progression free survival (PFS) measured applying immune related radiological criteria. PFS (RECIST) at 6 months and 1 year from initiation of Pembrolizumab.
- Overall survival
- 1, 2 and 3 year OS rate.
- Best overall response rate and disease control rate using both RECIST and irRC in patients with squamous and non-squamous NSCLC and
- Immune-related toxicities (IRAEs)

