4.2.1.2 Dose Modification (Escalation/Titration/Other)

Adverse events (both non-serious and serious) associated with pembrolizumab exposure may represent an immunologic etiology. These adverse events may occur shortly after the first dose or several months after the last dose of treatment. Pembrolizumab must be withheld for drug-related toxicities and severe or life-threatening AEs as per 3 below. See Section 5.6 for supportive care guidelines, including use of corticosteroids.

Table 3 Dose Modification Guidelines for Drug-Related Adverse Events

Toxicity	Hold Treatment For Grade	Timing for Restarting Treatment	Treatment Discontinuation
Diarrhea/Colitis	2-3	Toxicity resolves to Grade 0-1	Toxicity does not resolve within 12 weeks of last dose or inability to reduce corticosteroid to 10 mg or less of prednisone or equivalent per day within 12 weeks
	4	Permanently discontinue	Permanently discontinue
AST, ALT, or Increased Bilirubin	2	Toxicity resolves to Grade 0-1	Toxicity does not resolve within 12 weeks of last dose
	3-4	Permanently discontinue (see exception below) ^a	Permanently discontinue
Type 1 diabetes mellitus (if new onset) or Hyperglycemia	T1DM or 3-4	Hold pembrolizumab for new onset Type 1 diabetes mellitus or Grade 3-4 hyperglycemia associated with evidence of beta cell failure	Resume pembrolizumab when patients are clinically and metabolically stable
Hypophysitis	2-4	Toxicity resolves to Grade 0-1. Therapy with pembrolizumab can be continued while endocrine replacement therapy is instituted	Toxicity does not resolve within 12 weeks of last dose or inability to reduce corticosteroid to 10 mg or less of prednisone or equivalent per day within 12 weeks
Hyperthyroidism	3	Toxicity resolves to Grade 0-1	Toxicity does not resolve within 12 weeks of last dose or inability to reduce corticosteroid to 10 mg or less of prednisone or equivalent per day within 12 weeks
	4	Permanently discontinue	Permanently discontinue
Hypothyroidism		Therapy with pembrolizumab can be continued while thyroid replacement therapy is instituted	Therapy with pembrolizumab can be continued while thyroid replacement therapy is instituted
Infusion Reaction	2 ^b	Toxicity resolves to Grade 0-1	Permanently discontinue if toxicity develops despite adequate premedication
	3-4	Permanently discontinue	Permanently discontinue

Toxicity	Hold Treatment For Grade	Timing for Restarting Treatment	Treatment Discontinuation

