4.5.2 Prohibited Concomitant Medications

Subjects are prohibited from receiving the following therapies during the Screening and Treatment Phase (including retreatment for post-complete response relapse) of this trial:

- Antineoplastic systemic chemotherapy or biological therapy
- Immunotherapy not specified in this protocol
- Chemotherapy not specified in this protocol
- Investigational agents other than pembrolizumab
- Radiation therapy
 - Note: Radiation therapy to a symptomatic solitary lesion or to the brain may be allowed at the investigator's discretion.

- Live vaccines within 30 days prior to the first dose of trial treatment and while participating in the trial. Examples of live vaccines include, but are not limited to, the following: **measles, mumps, rubella, varicella/zoster, yellow fever, rabies, BCG, and typhoid vaccine.**
- Systemic glucocorticoids for any purpose other than to modulate symptoms from an event of clinical interest of suspected immunologic etiology. The use of physiologic doses of corticosteroids may be approved after consultation with the Sponsor.

Subjects who, in the assessment by the investigator, require the use of any of the aforementioned treatments for clinical management should be removed from the trial. Subjects may receive other medications that the investigator deems to be medically necessary.

The Exclusion Criteria describes other medications which are prohibited in this trial.

There are no prohibited therapies during the Post-Treatment Follow-up Phase.

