6.1.2.1 Adverse Event (AE) Monitoring

The investigator or qualified designee will assess each subject to evaluate for potential new or worsening AEs as specified in the Trial Flow Chart and more frequently if clinically indicated. Adverse experiences will be graded and recorded throughout the study and during the follow-up period according to NCI CTCAE Version 4.0 (see Section 11.2). Toxicities will be characterized in terms regarding seriousness, causality, toxicity grading, and action taken with regard to trial treatment.

For subjects receiving treatment with pembrolizumab all AEs of unknown etiology associated with pembrolizumab exposure should be evaluated to determine if it is possibly an event of clinical interest (ECI) of a potentially immunologic etiology (termed immune-related adverse events, or irAEs); see the separate ECI guidance document in Appendix 4 regarding the identification, evaluation and management of potential irAEs.

Please refer to section 7.2 for detailed information regarding the assessment and recording of AEs.

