From the time of treatment allocation/randomization through 30 days following cessation of treatment, all adverse events must be reported by the investigator. Such events will be recorded at each examination on the Adverse Event case report forms/worksheets. The reporting timeframe for adverse events meeting any serious criteria is described in section 7.2.3.1. The investigator will make every attempt to follow all subjects with non-serious adverse events for outcome.

6.2.1 Definition of an Overdose for This Protocol and Reporting of Overdose to the Sponsor and to Merck

For purposes of this trial, an overdose of pembrolizumab will be defined as any dose of 1,000 mg or greater (≥ 5 times the indicated dose). No specific information is available on the treatment of overdose of pembrolizumab. Appropriate supportive treatment should be provided if clinically indicated. In the event of overdose, the subject should be observed closely for signs of toxicity. Appropriate supportive treatment should be provided if clinically indicated.

If an adverse event(s) is associated with (“results from”) the overdose of a Merck product, the adverse event(s) is reported as a serious adverse event, even if no other seriousness criteria are met.

If a dose of Merck’s product meeting the protocol definition of overdose is taken without any associated clinical symptoms or abnormal laboratory results, the overdose is reported as a non-serious Event of Clinical Interest (ECI), using the terminology “accidental or intentional overdose without adverse effect.”

All reports of overdose with and without an adverse event must be reported within 24 hours to the Sponsor and within 2 working days hours to Merck Global Safety. (Attn: Worldwide Product Safety; [contact])

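### Late non-serious immune-related events are collected according to why the patient stopped, because the protocol gives conflicting rules on which irAEs it collects and for how long

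*Combined protocol and SAP*

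**What the plan says.** Section 3.2.3.1 lists "Immune-related toxicities (IRAEs") among the secondary endpoints. Section 7 covers only the primary endpoint and the sample size, so the irAE endpoint has no count rule and no time window.

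**Status of irAEs.** Section 6.1.2.1 asks whether an adverse event of unknown cause is "possibly an event of clinical interest (ECI) of a potentially immunologic etiology (termed immune-related adverse events, or irAEs"). Section 4.5.2 uses the term in the same way: "event of clinical interest of suspected immunologic etiology". The list in 6.2.3.2, introduced by "Events of clinical interest for this trial include", has two items: an overdose without symptoms or abnormal laboratory results, and a combined transaminase, bilirubin and alkaline phosphatase pattern.

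**Duration of collection.** Section 6.2 sets the general rule: "through 30 days following cessation of treatment, all adverse events must be reported by the investigator". Section 4.8 and the Safety Follow-Up Visit section (numbered 7.1.5.3.1) agree on about 30 days. ECIs under 6.2.3.2 run to 90 days, cut to 30 if new anticancer therapy starts. Section 6.1.2.1 also says that adverse events are recorded in the follow-up period, and the flow chart in 5.1 ticks adverse event review at the 9-weekly Follow Up Visits.

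**Expected timing.** Section 4.2.1.2 says of events that may be immunologic: "These adverse events may occur shortly after the first dose or several months after the last dose of treatment".

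**The concern.** The endpoint has no definition of its own, so the collection rules decide what it counts, and they point in different directions. Pneumonitis, colitis, hypophysitis, thyroid disease, nephritis and new diabetes are the events that Table 3 and 4.6.1 manage as immune-related. None of them is in the ECI list. Whether a non-serious case that starts after day 30 enters the data depends on which section a site follows and on why the patient stopped.

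The second dependence matters more for the analysis. If late events are looked for in patients who stop without progression and not in those who progress, the irAE rate mixes two levels of ascertainment, and reason for stopping is itself an outcome of the trial. The likely direction is understatement among patients who progress.

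There is a knock-on effect. Section 4.5.1 records concomitant medication beyond 30 days only for serious events and ECIs. If a late irAE is not an ECI, the corticosteroid course that would help to identify it need not be recorded either.

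**Working it through.** There is no planned figure to reproduce; the check sets the rules side by side.

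**Inputs**
- General adverse event window: 30 days after treatment (4.8, 6.2, 7.1.5.3.1).
- ECI window: 90 days, or 30 days once new therapy starts (6.2.3.2). The rules disagree over 90 − 30 = 60 days.
- Follow Up Visits: every 9 weeks, 9 × 7 = 63 days (± 7), only for patients who stop for a reason other than progression (6.1.5.4).
- After confirmed progression or new therapy: telephone contact every 12 weeks for survival status (6.1.5.4.1). The flow chart leaves adverse event review blank in that column.

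**Rules by patient group, for a non-serious irAE that starts after treatment ends**

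| Group | 30-day sections | Flow chart and 6.1.2.1 | If irAEs are ECIs |
|---|---|---|---|
| Stopped without progression, no new therapy | to day 30 | reviewed from about day 63 onward | to day 90 |
| Progressed, no new therapy | to day 30 | no scheduled review after the safety visit | to day 90, but no contact asks |
| Started new therapy | to day 30 | no scheduled review after the safety visit | to day 30 |

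**Test case.** Take a non-serious Grade 2 pneumonitis that starts on day 45.
- In the first group it falls outside the 30-day rule but would come up at the visit around day 63.
- In the second group it is reportable only if irAEs are ECIs, and no scheduled contact asks about it.
- In the third group no reading collects it.

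The same event is thus counted or not according to the reason for stopping. The third row also shows that adding irAEs to the ECI list would not by itself close the gap.

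**How many patients this could touch.** The plan's two hypotheses for one-year irPFS are 12% and 25%. With 48 patients, 48 × (1 − 0.25) = 36 and 48 × (1 − 0.12) = 42.24, so about 36 to 42 would not be progression-free at one year. This is only an order of magnitude. The count may include deaths, and patients whom 4.8 allows to stay on treatment after confirmed progression keep their cycle visits.

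**The case against.** The strongest reply is that the protocol already looks for late events. The flow chart schedules adverse event review at the 9-weekly visits, 6.1.2.1 confirms recording in follow-up, and patients who stop early for toxicity are among those who attend. This stands for patients who stop without progression. A reader might infer that every late non-serious irAE drops out at day 30; these two places do not support that. They do contradict the 30-day sections, and they do not reach patients who progress or start new therapy.

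Second, the ECI list may not be exhaustive. Its lead-in is open-ended, and 6.1.2.1 tells sites to "see the separate ECI guidance document in Appendix 4 regarding the identification, evaluation and management of potential irAEs". The appendices here are 10.1 to 10.3, so that guidance cannot be checked. It may name the immune-related categories. However, 4.5.1 and 6.1.1.4.2 point to the adverse event section (cited there as 7.2, now 6.2) for the definition of ECIs, so the rule belongs there. It would also go too far to say that the list can capture no irAE: item 2 applies whatever the cause, so an immune hepatitis that met all its limits would qualify.

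Third, ECI status governs expedited reporting, and irAEs could be tabulated from ordinary adverse event forms. That is true, but only for events that were collected.

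Fourth, related serious events are reportable at any time (6.2.3.1). This stands, and it limits the point to non-serious events.

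**Conclusion.** The point holds as a conflict between sections with a consequence for one secondary endpoint. Late non-serious irAEs, which the protocol itself expects, are ascertained according to the reason for stopping, and the irAE rate may be understated in patients who progress.

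The size can be given only as the 60-day stretch over which the rules differ. The documents do not say what share of irAEs start after day 30, so the number missed is unknown. Two stronger inferences are not supported:
- A reader might express 90 against 30 days as a trial-wide gain in observation time. That would ignore the existing Follow Up Visits and the cut to 30 days once new therapy starts.
- A reader might conclude that the window can be shorter than 30 days, because the safety visit is brought forward when new therapy begins. Section 6.2 still requires all adverse events through 30 days, with no such exception.

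The conclusion assumes that the flow chart ticks were read into the correct columns and that the unseen ECI guidance does not override 6.2.3.2. The endpoint is descriptive and no hypothesis test depends on it. I would class this as a cheap improvement.

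**What to change.** 1. Reconcile 4.8, 5.1, 6.1.2.1, 6.2, 6.2.3.2 and 7.1.5.3.1 on one collection window for non-serious adverse events.
2. State in 6.2.3.2 whether irAEs are ECIs, using the categories already in Table 3 and 4.6.1.
3. Define the secondary endpoint in Section 7 as the number and proportion of patients with at least one such event, by category and worst CTCAE grade, from first dose to 90 days after the last dose, whatever the reason for stopping.
4. Collect these events at the existing Follow Up Visits and, for patients in survival follow-up, through a question at the existing telephone contact. If the 12-week calls are counted from discontinuation, the first falls at 12 × 7 = 84 days, so the question must be asked again at the next contact to complete the 90 days.
5. Report events that start after new anticancer therapy separately.

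Step 2 alone is not enough, because the ECI window falls to 30 days once new therapy begins. The cost is a few sentences of text, one telephone question, somewhat more adverse event reporting and possibly a slightly higher stated toxicity rate. No extra visit is needed.

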6.2.3.3 Protocol-Specific Exceptions to Serious Adverse Event Reporting

Efficacy endpoints as outlined in this section will not be reported to Merck as described in Section 7.2.3- Immediate Reporting of Adverse Events to the Sponsor and to Merck, unless there is evidence suggesting a causal relationship between the drug and the event. Any such event will be submitted to the Sponsor within 24 hours and to Merck Global Safety within 2 working days either by electronic or paper media.

Specifically, the suspected/actual events covered in this exception include any event that is disease progression of the cancer under study.

The Sponsor will monitor unblinded aggregated efficacy endpoint events and safety data to ensure the safety of the subjects in the trial. Any suspected endpoint which upon review is not progression of the cancer under study will be forwarded to Merck Global Safety as a SAE within 2 working days of determination that the event is not progression of the cancer under study.

Hospitalization related to convenience (e.g. transportation issues etc.) will not be considered a SAE.

6.2.4 Evaluating Adverse Events

An investigator who is a qualified physician will evaluate all adverse events according to the NCI Common Terminology for Adverse Events (CTCAE), version 4.0. Any adverse event which changes CTCAE grade over the course of a given episode will have each change of grade recorded on the adverse event case report forms/worksheets.

All adverse events regardless of CTCAE grade must also be evaluated for seriousness.

Table 6 Evaluating Adverse Events

An investigator who is a qualified physician, will evaluate all adverse events as to:

V4.0 CTCAE Grading	Grade 1	Mild; asymptomatic or mild symptoms; clinical or diagnostic observations only; intervention not indicated.
	Grade 2	Moderate; minimal, local or noninvasive intervention indicated; limiting age-appropriate instrumental ADL.
	Grade 3	Severe or medically significant but not immediately life-threatening; hospitalization or prolongation of hospitalization indicated; disabling; limiting self-care ADL.
	Grade 4	Life threatening consequences; urgent intervention indicated.
	Grade 5	Death related to AE
Seriousness	A serious adverse event is any adverse event occurring at any dose or during any use of Merck product that:	
	† Results in death; or	
	† Is life threatening; or places the subject, in the view of the investigator, at immediate risk of death from the event as it occurred (Note: This does not include an adverse event that, had it occurred in a more severe form, might have caused death.); or	
	† Results in a persistent or significant disability/incapacity (substantial disruption of one's ability to conduct normal life functions); or	
	† Results in or prolongs an existing inpatient hospitalization (hospitalization is defined as an inpatient admission, regardless of length of stay, even if the hospitalization is a precautionary measure for continued observation. (Note: Hospitalization for an elective procedure to treat a pre-existing condition that has not worsened is not a serious adverse event. A pre-existing condition is a clinical condition that is diagnosed prior to the use of a Merck product and is documented in the patient's medical history.); or	
	† Is a congenital anomaly/birth defect (in offspring of subject taking the product regardless of time to diagnosis); or	
	Is a new cancer (that is not a condition of the study) (although not serious per ICH definition, is reportable to the Sponsor within 24 hours and to Merck within 2 working days to meet certain local requirements); or	
	Is an overdose (whether accidental or intentional). Any adverse event associated with an overdose is considered a serious adverse event for collection purposes. An overdose that is not associated with an adverse event is considered a non-serious event of clinical interest and must be reported within 24 hours to the Sponsor and to Merck within 2 working days..	
	Other important medical events that may not result in death, not be life threatening, or not require hospitalization may be considered a serious adverse event when, based upon appropriate medical judgment, the event may jeopardize the subject and may require medical or surgical intervention to prevent one of the outcomes	

	listed previously (designated above by a †).
Duration	Record the start and stop dates of the adverse event. If less than 1 day, indicate the appropriate length of time and units
Action taken	Did the adverse event cause Merck product to be discontinued?
Relationship to Merck Product	
Did Merck product cause the adverse event? The determination of the likelihood that Merck product caused the adverse event will be provided by an investigator who is a qualified physician. The investigator's signed/dated initials on the source document or worksheet that supports the causality noted on the AE form, ensures that a medically qualified assessment of causality was done. This initialed document must be retained for the required regulatory time frame. The criteria below are intended as reference guidelines to assist the investigator in assessing the likelihood of a relationship between the test drug and the adverse event based upon the available information.
 
The following components are to be used to assess the relationship between Merck product and the AE; the greater the correlation with the components and their respective elements (in number and/or intensity), the more likely Merck product caused the adverse event (AE):

Exposure	Is there evidence that the subject was actually exposed to Merck product such as: reliable history, acceptable compliance assessment (pill count, diary, etc.), expected pharmacologic effect, or measurement of drug/metabolite in bodily specimen?
Time Course	Did the AE follow in a reasonable temporal sequence from administration of Merck product? Is the time of onset of the AE compatible with a drug-induced effect (applies to trials with investigational medicinal product)?
Likely Cause	Is the AE not reasonably explained by another etiology such as underlying disease, other drug(s)/vaccine(s), or other host or environmental factors

Relationship to Merck Product (continued)		The following components are to be used to assess the relationship between the test drug and the AE: (continued)	
	Dechallenge	
Was Merck product discontinued or dose/exposure/frequency reduced?
 
If yes, did the AE resolve or improve?
 
If yes, this is a positive dechallenge. If no, this is a negative dechallenge.
 
(Note: This criterion is not applicable if: (1) the AE resulted in death or permanent disability; (2) the AE resolved/improved despite continuation of the Sponsor's product; or (3) the trial is a single-dose drug trial); or (4) Sponsor's product(s) is/are only used one time.)
	
	Rechallenge	
Was the subject re-exposed to Merck product in this study?
 
If yes, did the AE recur or worsen?
 
If yes, this is a positive rechallenge. If no, this is a negative rechallenge.
 
(Note: This criterion is not applicable if: (1) the initial AE resulted in death or permanent disability, or (2) the trial is a single-dose drug trial); or (3) Sponsor's product(s) is/are used only one time).
 
NOTE: IF A RECHALLENGE IS PLANNED FOR AN ADVERSE EVENT WHICH WAS SERIOUS AND WHICH MAY HAVE BEEN CAUSED BY MERCK PRODUCT, OR IF REEXPOSURE TO MERCK PRODUCT POSES ADDITIONAL POTENTIAL SIGNIFICANT RISK TO THE SUBJECT, THEN THE RECHALLENGE MUST BE APPROVED IN ADVANCE BY THE SPONSOR AS PER DOSE MODIFICATION GUIDELINES IN THE PROTOCOL.
	
	Consistency with Trial Treatment Profile	Is the clinical/pathological presentation of the AE consistent with previous knowledge regarding Merck product or drug class pharmacology or toxicology?	
The assessment of relationship will be reported on the case report forms /worksheets by an investigator who is a qualified physician according to his/her best clinical judgment, including consideration of the above elements.			
Record one of the following		Use the following scale of criteria as guidance (not all criteria must be present to be indicative of Merck product relationship).	
Yes, there is a reasonable possibility of Merck product relationship.		There is evidence of exposure to Merck product. The temporal sequence of the AE onset relative to the administration of Merck product is reasonable. The AE is more likely explained by Merck product than by another cause.	
No, there is not a reasonable possibility of Merck product relationship		Subject did not receive the Merck product OR temporal sequence of the AE onset relative to administration of Merck product is not reasonable OR the AE is more likely explained by another cause than the Merck product. (Also entered for a subject with overdose without an associated AE.)	

